**Protocol/Amendment No.:**

Study Calendar Notes:

A Safety follow up: For all patients (responders and non-responders) at 30 days (+/- 10 days) following cycle 8 pembrolizumab on study.

B Follow up visits: For all responder patients only every 12 weeks (+/- 14 days) following cycle 4 pembrolizumab on study. Will include correlative stool sampling.

C Survival follow up visits: For all patients (responders and non-responders) every 12 weeks (+/- 14 days) following cycle 8 pembrolizumab on study

D Patients self-monitoring: while on study, patients will be provided a memory card and digital thermometer to facilitate the standardized collection of AEs particularly AEs commonly associated with FMT including fever, diarrhea, vomiting, abdominal discomfort, constipation, and flatulence.

E CBC w/diff, Comprehensive Serum Chemistry Panel (allowed within 28 days)

F PT/INR and aPTT; urinalysis; Pregnancy Test; Stool and Blood Screening (allowed within 28 days)

G FT4 and TSH (allowed within 28 days) To be repeated at every odd cycle.

H Restaging imaging will be obtained after 4 cycles of therapy (12 weeks) comprising of CT or PET/CT imaging. Scans will be repeated every 12 weeks. If CNS lesions were present at staging, restaging imaging should include MRI brain or CT head with contrast. If CNS lesions were not present at staging scans, this need not be repeated.

I Correlative laboratory studies will be performed at Screening, during each cycle (Cycles 1-8) and q12 weekly afterwards till EOT.

J Correlative stool studies will be performed at Screening, weekly (Cycles 1-8), and q6 weekly afterwards till EOT.

K Following FMT, dietary history questionnaire (Appendix 3) will be monitored q12 weekly afterwards till EOT.

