- a. Understand infectious risks associated with FMT administration. Although FMT infusate has been screened for bacteria, viruses, fungi and parasites there is a risk of transmission of known and unknown infectious organisms contained in the donor stool. Post-FMT bacteremia (e.g. E. coli), sepsis and fatal events may rarely occur.
  - b. Understand non-infectious risks associated with FMT administration.
    - i. Possible allergy and/or anaphylaxis to antigens in donor stool.
    - ii. Theoretical risk of developing disease possibly related to donor gut microbiota including but not limited to: obesity, metabolic syndrome, cardiovascular disease, autoimmune conditions, allergic/atopic disorders, neurologic disorders, psychiatric conditions and malignancy.
  - c. Understand risks associated with colonoscopy including risk of infection transmission, colonic perforation, aspiration pneumonia, and death.
  - d. Understand that data regarding the long-term safety risk of FMT are lacking.
7. Amenable to participate in the correlative studies and should have available tumor tissue for tumor biopsies. Acceptable biopsies include surgical biopsy, core biopsy or punch/surgical tumor biopsies (of accessible lesions).
8. Have measurable disease as per RECIST version 1.1. At least 1 of the tumor sites must be amenable to biopsy and this may not be the site of disease used to measure antitumor response.
9. Be willing and able to provide written informed consent for the trial.
10. Be  $\geq 18$  years of age on day of signing informed consent.
11. Have a performance status of 0 or 1 on the ECOG Performance Scale.
12. Demonstrate adequate organ function as defined in **Table 5.1.1**, all screening labs should be performed within 14 days of treatment initiation.

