**Table 5.1.1-1 Adequate Organ Function Laboratory Values**

System	Laboratory Value
--------	------------------

Hematological	
Absolute neutrophil count (ANC)	≥1,500 /mcL
Platelets	≥100,000 / mcL
Hemoglobin	≥9 g/dL or ≥5.6 mmol/L without transfusion or EPO dependency (within 7 days of assessment)
Renal	
Serum creatinine OR Measured or calculated a creatinine clearance (GFR can also be used in place of creatinine or CrCl)	≤1.5 X upper limit of normal (ULN) OR ≥60 mL/min for subject with creatinine levels > 1.5 X institutional ULN
Hepatic	
Serum total bilirubin	≤ 1.5 X ULN OR Direct bilirubin ≤ ULN for subjects with total bilirubin levels > 1.5 ULN
AST (SGOT) and ALT (SGPT)	≤ 2.5 X ULN OR ≤ 5 X ULN for subjects with liver metastases
Albumin	≥2.5 mg/dL
Coagulation	
International Normalized Ratio (INR) or Prothrombin Time (PT) Activated Partial Thromboplastin Time (aPTT)	≤1.5 X ULN unless subject is receiving anticoagulant therapy as long as PT or PTT is within therapeutic range of intended use of anticoagulants
a Creatinine clearance should be calculated per institutional standard.	

13. Female subject of childbearing potential should have a negative urine or serum pregnancy within 72 hours prior to receiving the first dose of study medication. If the urine test is positive or cannot be confirmed as negative, a serum pregnancy test will be required.

14. Female subjects of childbearing potential (Section 5.7.2) must be willing to use an adequate method of contraception as outlined in Section 5.7.2 – Contraception, for the course of the study through 120 days after the last dose of study medication.

Note: Abstinence is acceptable if this is the usual lifestyle and preferred contraception for the subject.

15. Male subjects of childbearing potential (Section 5.7.1) must agree to use an adequate method of contraception as outlined in Section 5.7.1- Contraception, starting with the first dose of study therapy through 120 days after the last dose of study therapy.

Note: Abstinence is acceptable if this is the usual lifestyle and preferred contraception for the subject.

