**Protocol/Amendment No.:**

Trial Period:	Screening Phase	Treatment Cycles a								End of Treatment	Post-Treatment		
		1*	2*	3*	4*	To be repeated beyond 4 cycles					Discontinuation	Safety Follow-up A	Follow Up Visits B
Treatment Cycle/Title:	Study Screening (Visit 1)	5*	6*	7*	8+*								
Scheduling Window (Days):	-28 to -1	± 3	± 3	± 3	± 3	± 3	± 3	± 3	± 3	At time of discontinuation	30 days post discontinuation	Every 12 weeks	Every 12 weeks
Screening labs prior to FMT administration (see Appendix 2)	+												
Laboratory Procedures/Assessments: analysis performed by LOCAL laboratory													
Hematology and serum chemistry E	+	+	+	+	+	+	+	+	+				
Coagulation studies and urinalysis F	+												
Thyroid studies G	+	+		+		+		+					
Efficacy Measurements													
Tumor Imaging H	+				+				+				
CNS Imaging (if not previously performed) *CNS imaging will be incorporated into restaging assessments if prior CNS disease is known/stable H	+*				+				+				
Tumor Biopsies; Archival Tissue Collection; Correlative Studies Blood/Stool													
Tissue Collection (pre-treatment and C4; biopsy at progression is optional)	+				+								
Correlative studies (blood) I	+	+	+	+	+	+	+	+	+(q12)			+	
Correlative studies (stool) J	+	+	+	+	+	+	+	+	+(q6)			+	
Dietary questionnaire (Appendix 3) K	+	+	+	+	+	+	+	+	+(q12)				

**Product:** Pembrolizumab  

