## **8.5. Analysis Plan**

### **8.5.1. Decision Rule and Sample Size Justification**

#### **8.5.1.1. Patient Evaluability and Definition of Objective Response**

All patients meeting the eligibility criteria who have signed a consent form and begun pembrolizumab and/or FMT will be considered evaluable for estimation of the response probability. For evaluable patients, objective response will be assessed by RECIST 1.1.

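### Calendar notes E and F allow 28 days for tests that inclusion criteria 12 and 13 require within 14 days or 72 hours, and the albumin floor is printed in a doubtful unit

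*Combined protocol and SAP*

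**What the plan says.** **Eligibility criteria (Section 5.1.1).** Criterion 12 covers the organ-function values in Table 5.1.1-1 (hematology, renal, hepatic including albumin, and coagulation) and states that "all screening labs should be performed within 14 days of treatment initiation". Criterion 13 asks women of childbearing potential for a "negative urine or serum pregnancy within 72 hours prior to receiving the first dose of study medication". The Second Course Phase (Section 7.1.5.7) repeats the 72-hour requirement for retreatment and then refers to the flow chart for its visits.

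**Study calendar (Section 6.0).** Note E reads "CBC w/diff, Comprehensive Serum Chemistry Panel (allowed within 28 days". Note F names PT/INR, aPTT and urinalysis, then continues "Pregnancy Test; Stool and Blood Screening (allowed within 28 days". Note F belongs to the row "Coagulation studies and urinalysis", which is marked at screening only. The hematology and chemistry row, which carries note E, is marked at screening and at every cycle from cycle 1. Screening runs from day -28 to day -1, both in the calendar and in Section 7.1.5.2.

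**Albumin (Table 5.1.1-1).** The floor is printed as 2.5 mg/dL. The hemoglobin floor in the same table is 9 g/dL.

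**The concern.** Sections 7.1, 7.1.5, 7.1.5.2 and 7.1.5.3 send staff to the flow chart for what to do at each visit. Someone who follows it faithfully can dose a patient on a pregnancy or coagulation result that is too old for the inclusion criteria, without having departed from the calendar.

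Section 5.7.2 warns that pembrolizumab may harm a fetus, so the age of the pregnancy test bears on safety. Section 2.1 has FMT given endoscopically with an intestinal biopsy, so the coagulation result bears on that procedure. At the least, such a patient is an eligibility deviation that the protocol's own schedule produced.

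The albumin unit raises a different question: a floor set far below any plausible value screens nobody.

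**Working it through.** The plan states no figure on this point to reproduce. The check sets the windows side by side and converts one unit. Day -n is taken as n days before the first dose.

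**1. Windows**

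| Test | Criterion | Calendar note | Calendar marks up to cycle 1 |
|---|---|---|---|
| Blood count, chemistry | 14 days (12) | 28 days (E) | Screening and cycle 1 |
| PT/INR, aPTT | 14 days (12) | 28 days (F) | Screening only |
| Pregnancy test | 72 hours (13) | 28 days (F) | Screening only |

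**2. Size of the gaps**

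- Laboratory tests: 28 / 14 = 2. Days -28 to -15 pass the calendar and fail criterion 12: 28 - 14 = 14 of the 28 screening days.
- Pregnancy test: 28 × 24 = 672 hours, and 672 / 72 = 9.3. Since 72 hours is 3 days, days -28 to -4 pass the calendar and fail criterion 13: 28 - 3 = 25 of the 28 screening days.

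**3. Is the gap closed elsewhere?**

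For blood count and chemistry, largely yes. Section 5.2.2 has treatment given after the flow-chart assessments are complete, and this row is marked at cycle 1, so a recent sample would normally exist. For coagulation and the pregnancy test, the visible calendar has no mark after screening.

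**4. Albumin**

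2.5 mg/dL ÷ 1000 = 0.0025 g/dL. The documents give no albumin range. Assuming 1 to 5 g/dL:

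- 1 g/dL = 1000 mg/dL, and 1000 / 2.5 = 400 times the floor
- 5 g/dL = 5000 mg/dL, and 5000 / 2.5 = 2000 times the floor

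Over that whole range nobody falls below the floor.

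**5. Error rates**

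The rule in Section 8.5.1.2 stops at 0 of 13 and declares the treatment promising at 3 or more of 20. The probability of a promising result at response rate p is the sum over x = 1 to 13 of P(X = x) × P(Y ≥ 3 - x), with X ~ Bin(13, p) and Y ~ Bin(7, p). It is 0.0736 at p = 0.05 and 0.903 at p = 0.25, in line with the stated 0.07 and 90%. No test window enters the formula.

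**The case against.** **The tighter window satisfies both rules.** Section 5.1.1 requires every criterion to be met, Section 7.1.1.2 has the investigator review them all, and Section 7.1 says that the flow chart only summarizes procedures. Omitting the 72-hour test breaches criterion 13 whatever note F allows. This stands: a reader might infer that the eligibility checks cannot be operated, and the documents do not support that. Still, no section ranks the two rules, and the schedule staff work from shows the looser one.

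**The calendar is incomplete in the available text.** Note D has no visible row, and the vital-signs and performance-status rows that Sections 7.1.2.4 and 7.1.2.5 place there are absent. A separate pregnancy-test row cannot be excluded, so one may not conclude that no test is scheduled near dosing. Note F's 28 days conflicts with criterion 13 either way.

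**Nothing shows that a 28-day-old coagulation result would mislead.** This is true. The point is that the protocol sets 14 days and then allows 28.

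**Thyroid tests.** Note G, "FT4 and TSH (allowed within 28 days", might look like a further conflict. Thyroid tests are not in Table 5.1.1-1, and they are marked again at cycle 1, so they are not counted here.

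**Response-rate bias.** Section 8.5.1.1 says "All patients meeting the eligibility criteria who have signed a consent form and begun pembrolizumab and/or FMT will be considered evaluable", and a reader might infer that patients with late tests could be dropped from the response rate once their outcome is known. No section provides for that, and Section 7.1.5.3 has the Principal Investigator decide eligibility before treatment. Criterion 12 says that labs should fall within 14 days, so a late test may be only a deviation. The inference is not supported.

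**Conclusion.** The contradiction is real and should be removed. It affects blood count, chemistry, coagulation and the pregnancy test, and has most practical weight for the last two. The calendar accepts a pregnancy test up to 9.3 times as old as criterion 13 permits, and laboratory tests up to twice as old as criterion 12 permits. The consequence is a patient-safety question and avoidable eligibility deviations; the type I error rate and power are untouched.

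That coagulation and the pregnancy test are not rescheduled near dosing rests on the visible part of the calendar. The conflict between the stated windows does not.

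The albumin floor looks like a unit error. That it would exclude nobody depends on the assumed range of 1 to 5 g/dL, and the hemoglobin unit in the same table makes a slip plausible. Only the sponsor can confirm the intended unit.

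**What to change.** - Reconcile criteria 12 and 13 with calendar notes E and F so that each test has one window, as the sponsor intends. State it once in Section 5.1.1 and have the notes refer to it.
- Mark the calendar so that each test falls where its window can be met. Separating the pregnancy test from the coagulation and urinalysis row would let it carry its own timing. Keep Section 7.1.5.7 consistent with the result.
- Have the sponsor confirm the albumin unit in Table 5.1.1-1 and correct it if it is wrong.

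The cost is wording in Section 5.1.1, its table and the calendar, submitted as a protocol modification for the IRB approval that Section 10.8 requires. If the sponsor keeps the criteria's windows, the only added procedures are tests that those criteria already demand. Sample size and analysis do not change.

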## **7.0 TRIAL PROCEDURES**

### **7.1 Trial Procedures**

The Trial Flow Chart - Section 6.0 summarizes the trial procedures to be performed at each visit. Individual trial procedures are described in detail below. It may be necessary to perform these procedures at unscheduled time points if deemed clinically necessary by the investigator.

Furthermore, additional evaluations/testing may be deemed necessary by the Principal Investigator and/or Sponsor and/or Merck for reasons related to subject safety. In some cases, such evaluation/testing may be potentially sensitive in nature (e.g., HIV, Hepatitis C, etc.), and thus local regulations may require that additional informed consent be obtained from the subject. In these cases, such evaluations/testing will be performed in accordance with those regulations.

#### **7.1.1 Administrative Procedures**

##### **7.1.1.1 Informed Consent**

The Investigator must obtain documented consent from each potential subject prior to participating in a clinical trial.

##### **7.1.1.1.1 General Informed Consent**

Consent must be documented by the subject's dated signature or by the subject's legally acceptable representative's dated signature on a consent form along with the dated signature of the person conducting the consent discussion.

A copy of the signed and dated consent form should be given to the subject before participation in the trial.

The initial informed consent form, any subsequent revised written informed consent form and any written information provided to the subject must receive the IRB approval in advance of use. The subject or his/her legally acceptable representative should be informed in a timely manner if new information becomes available that may be relevant to the subject's willingness to continue participation in the trial. The communication of this information will be provided and documented via a revised consent form or addendum to the original consent form that captures the subject's dated signature or by the subject's legally acceptable representative's dated signature.

Specifics about a trial and the trial population will be added to the consent form template at the protocol level.

The informed consent will adhere to IRB requirements, applicable laws and regulations and Sponsor requirements.

### **7.1.1.2 Inclusion/Exclusion Criteria**

All inclusion and exclusion criteria will be reviewed by the investigator or qualified designee to ensure that the subject qualifies for the trial.

### **7.1.1.3 Medical History**

A medical history will be obtained by the investigator or qualified designee. Medical history will include all active conditions, and any condition diagnosed within the prior 10 years that are considered to be clinically significant by the Investigator. Details regarding the disease for which the subject has enrolled in this study will be recorded separately and not listed as medical history.

### **7.1.1.4 Prior and Concomitant Medications Review**

#### **7.1.1.4.1 Prior Medications**

The investigator or qualified designee will review prior medication use, including any protocol-specified washout requirement, and record prior medication taken by the subject within 28 days before starting the trial. Treatment for the disease for which the subject has enrolled in this study will be recorded separately and not listed as a prior medication.

#### **7.1.1.4.2 Concomitant Medications**

The investigator or qualified designee will record medication, if any, taken by the subject during the trial. This will include the intake of any oral antibiotic(s) for any indication. All medications related to reportable SAEs and ECIs should be recorded as defined in Section 7.2.

### **7.1.1.5 Disease Details and Treatments**

#### **7.1.1.5.1 Disease Details**

The investigator or qualified designee will obtain prior and current details regarding disease status.

#### **7.1.1.5.2 Prior Treatment Details**

The investigator or qualified designee will review all prior cancer treatments including systemic treatments, radiation and surgeries.

#### **7.1.1.5.3 Subsequent Anti-Cancer Therapy Status**

The investigator or qualified designee will review all new anti-neoplastic therapy initiated after the last dose of trial treatment. If a subject initiates a new anti-cancer therapy within 30 days after the last dose of trial treatment, the 30 day Safety Follow-up visit must occur before

the first dose of the new therapy. Once new anti-cancer therapy has been initiated the subject will move into survival follow-up.

#### **7.1.1.6 Assignment of Screening Number**

Not applicable.

#### **7.1.1.7 Assignment of Randomization Number**

Not applicable.

#### **7.1.1.8 Trial Compliance (Medication/Diet/Activity/Other)**

Antibiotic use and/or intake of probiotics is discouraged. Use will be recorded.

### **7.1.2 Clinical Procedures/Assessments**

#### **7.1.2.1 Adverse Event (AE) Monitoring**

The investigator or qualified designee will assess each subject to evaluate for potential new or worsening AEs as specified in the Trial Flow Chart and more frequently if clinically indicated. Adverse experiences will be graded and recorded throughout the study and during the follow-up period according to NCI CTCAE Version 5.0 (see Section 11.2). Toxicities will be characterized in terms regarding seriousness, causality, toxicity grading, and action taken with regard to trial treatment.

Please refer to section 7.2 for detailed information regarding the assessment and recording of AEs.

#### **7.1.2.2 Full Physical Exam**

The investigator or qualified designee will perform a complete physical exam during the screening period. Clinically significant abnormal findings should be recorded as medical history. A full physical exam should be performed during screening,

#### **7.1.2.3 Directed Physical Exam**

For cycles that do not require a full physical exam per the Trial Flow Chart, the investigator or qualified designee will perform a full physical exam as clinically indicated prior to trial treatment administration.

#### **7.1.2.4 Vital Signs**

Vital signs will be taken at screening, prior to the administration of each dose of trial treatment and at treatment discontinuation as specified in the Trial Flow Chart (Section 6.0). Vital signs should include temperature, pulse, respiratory rate, weight and blood pressure. Height will be measured at screening only.

#### **7.1.2.5 Eastern Cooperative Oncology Group (ECOG) Performance Scale**

The investigator or qualified designee will assess ECOG status (see Section 11.1) at screening, prior to the administration of each dose of trial treatment and discontinuation of trial treatment as specified in the Trial Flow Chart.

#### **7.1.2.6 Tumor Imaging and Assessment of Disease**

On this study, response will be first assessed after FMT administration and 4 cycles of pembrolizumab (cycle 4; week 21-22) and after cycle 8 (week 33-34). Assessment of antitumor response will be based on RECIST 1.1. Because tumor pseudo-progression is a well-recognized consequence of PD-1 based immunotherapies **and use of FMT as a therapeutic agent in cancer is highly novel**, confirmation of PD requires continued presence of PD on 2 consecutive assessments of response done at least 4 weeks apart during which pembrolizumab will be continued.

Computed tomography (CT) of chest, abdomen, pelvis and CT/MRI brain scans (if clinically indicated) will be performed at screening and after cycle 4 (Day 1  $\pm$  7 days). Following cycle 4, reimaging will occur every 4 cycles (12 weeks) starting with cycle 8 (cycles 12, 16, 20 etc.).

PD documented at any evaluation time point **will be followed** with a repeated radiographic evaluation at the Principal Investigator's discretion to rule out tumor pseudo-progression.

#### **7.1.2.7 Tumor Tissue Collection and Correlative Studies Blood/Stool Sampling**

Tumor biopsies will be performed at screening (Day -21 to -1) and at cycle 4 (Day 1  $\pm$  7 days). Surgical, core, or punch biopsies are permitted. Post-progression tumor biopsy is recommended but not required.

Correlative blood samples will be obtained as directed in Table 6.1 (Screening, cycles 1-8 and every 12 weeks starting after cycle 9 (Day 1  $\pm$  3 days)).

Correlative stool samples along with dietary history questionnaire will be obtained as directed in Table 6.1 (Screening, weekly cycles 1-8 and every 6 weeks starting after cycle 9 (Day 1  $\pm$  3 days)).

#### **7.1.3 Laboratory Procedures/Assessments**

Details regarding specific laboratory procedures/assessments to be performed in this trial are provided below.

Laboratory tests for hematology, chemistry, urinalysis, and others are specified in Table 7.1.3.

Prior to receiving FMT, specific laboratory tests to screen for infectious etiologies will be performed as listed in **Appendix 2**. Results of this must be available prior to FMT administration.

